2.1. Study Objectives

2.1.1. Primary Objective

The primary objective of the study is to evaluate the efficacy of dasiglucagon administered as a subcutaneous (SC) infusion in reducing hypoglycemia in children with congenital hyperinsulinism (CHI).

2.1.2. Secondary Objectives

The secondary objectives of the study are:

- To evaluate the safety and tolerability of dasiglucagon administered as an SC infusion in children with CHI
- To evaluate the efficacy of dasiglucagon in reducing glucose requirements
- To investigate quality of life and resource utilization

2.2. Study Endpoints

2.2.1. Efficacy Endpoints

2.2.1.1. Primary Efficacy Endpoint

The primary efficacy endpoint of this study is:

Treatment Period 1

- SMPG-detected hypoglycemia episode rate, defined as average weekly number of hypoglycemia episodes (plasma glucose [PG] <70 mg/dL or 3.9 mmol/L) during Weeks 2-4, as detected by self-monitored plasma glucose (SMPG).

2.2.1.2. Key Secondary Efficacy Endpoints

Key secondary efficacy endpoints of this study include the following:

Treatment Period 1

- Increase in fasting tolerance (time from beginning of meal to the beginning of the first continuous 15-minute CGM reading <70 mg/dL [3.9 mmol/L]).
- CGM percent time in range 70-180 mg/dL (3.9-10.0 mmol/L) during Weeks 2-4.
- Clinically significant SMPG-detected hypoglycemia episode rates, defined as average weekly number of episodes <54 mg/dL (3.0 mmol/L), as detected by SMPG during Weeks 2-4.

2.2.1.3. Secondary Efficacy Endpoints

Treatment Period 1

- Endpoints to be analyzed on the subgroup of patients having Gastrostomy or NG-tube at screening:
 - Total amount of gastric carbohydrates administered (via nasogastric [NG] tube or gastrostomy) per week to treat hypoglycemia during Weeks 2-4.
 - Rate of gastric carbohydrate administrations (NG tube or gastrostomy) per week to treat hypoglycemia during Weeks 2-4.
 - Amount of nightly (midnight to 6 am) gastric carbohydrates administered (NG tube or gastrostomy) per week during Weeks 2-4.
 - Total amount of gastric carbohydrates administered (NG tube or gastrostomy) per week during Weeks 2-4.
- Endpoints to be analyzed on whole population:
 - Extent of hypoglycemia (area over the glucose curve [AOC_{glucose}] below 70 mg/dL [3.9 mmol/L]) as measured by CGM during Weeks 2-4.
 - Extent of hypoglycemia (area over the glucose curve [AOC_{glucose}] below 54 mg/dL [3.9 mmol/L]) as measured by CGM during Weeks 2-4.

- CGM percent time in hypoglycemia (<70 mg/dL or 3.9 mmol/L) during Weeks 2-4.
- CGM-detected hypoglycemia episode rate, defined as number of episodes <70 mg/dL (3.9 mmol/L) for 15 minutes or more per week, as measured by CGM during Weeks 2-4.

Treatment Period 2

- Endpoints to be analyzed on the subgroup of patients having Gastrostomy or NG-tube at screening:
 - Rate of weekly number of gastric carbohydrate administrations (NG tube or gastrostomy) per week to treat hypoglycemia during Weeks 6-8.
- Endpoints to be analyzed on whole population:
 - CGM percent time in hypoglycemia (<70 mg/dL or 3.9 mmol/L) during Weeks 6-8.
 - SMPG-detected hypoglycemia episode rate, defined as number of episodes (PG <70 mg/dL or 3.9 mmol/L) per week during Weeks 6-8, as detected by SMPG.
 - Clinically significant CGM-detected hypoglycemia episode rate, defined as number of episodes <54 mg/dL (3.0 mmol/L) for 15 minutes or more per week, as measured by CGM during Weeks 6-8.

2.2.2.4 Other Efficacy Endpoints

- Number of intravenous (IV) glucose infusions to treat hypoglycemia per week during Weeks 2-4 of Treatment Period 1.
- Emergency department visits for hypoglycemia.
- Number and length of hospitalizations due to CHI or CHI-related events.
- Number of out-patient visits to health care providers (family doctors, specialist, etc.) caused by CHI or CHI-related events.
- Number of home visits by paramedics due to hypoglycemia.
- Quality of life endpoints (Pediatric Quality of Life Inventory™ [PedsQL] [Total Scale Score, Physical Health Summary Score, and Psychosocial Health Summary Score] and CHI-specific questionnaire).
- Rate of SMPG readings per week during Weeks 2-4 of Treatment Period 1.

2.2.2. Safety Endpoints

The safety endpoints of this study include the following:

- Adverse events (AEs)
- Changes in clinical evaluations:
 - Vital signs
 - Physical examination
 - 12-lead electrocardiogram (ECG)
- Changes for clinical laboratory assessments:

- Hematology
- Biochemistry
- Antidrug antibodies (ADAs)

2.2.3. Pharmacokinetics

Blood samples will be collected twice during the trial to measure for dasiglucagon levels at steady-state on Weeks 6 and 9.

3. Overall Study Design and Plan

[figure not shown]
This is a phase 3, 2-period open-label study for the treatment of patients with CHI. The objective of this to evaluate the efficacy and safety of dasiglucagon in children between the ages of 3 months and 12 years who experience ≥ 3 hypoglycemia episode per week despite receiving standard of care (SOC). Approximately 32 patients will be included in this study. Patients meeting entry criteria into the study will have to complete a 2-week CGM period to establish plasma glucose baseline. Once this is complete, the patients are randomized in a 1:1 ratio to continue receiving SOC alone or dasiglucagon + SOC for 4 weeks in Treatment Period 1. In Treatment Period 2, all patients will receive dasiglucagon + SOC for 4 weeks.

All patients will be hospitalized for 1-2 days and trained in using CGM sensor and glucometer. Participants who are randomly assigned to dasiglucagon + SOC will have dasiglucagon infusion initiated and titrated and be trained with infusion pump. Patients who were assigned to SOC alone during Treatment Period 1 will be hospitalized for 1-2 days in Week 5 of Treatment Period 2 to have dasiglucagon infusion initiated and titrated.

No interim analysis is planned (see section 10 on changes from planned analysis).

The maximum study duration for each patient is approximately 16 weeks. The dasiglucagon treatment duration varies between 4 or 8 weeks for each patient. [Figure 1](#) describes the study design. Patients completing the study will have choice to continue long-term trial for dasiglucagon treatment. If the patient chooses not to enter the extension trial, the study will end with a follow-up visit. The overall study design is expected to be 15 months. There will be screening which will last from 14-28 days followed by Treatment Period 1 for 4 weeks. This is followed by Treatment Period 2 and follow-up, each consisting of 4 weeks.

Figure 1: Study Design

3.1. Overall Design

3.2. Sample Size and Power

A total of up to 32 patients will be randomized if they have at least 3 events of hypoglycemia on average per week, as recorded in the diary during the 2 weeks prior to randomization. It is assumed that patients continuing on SOC will maintain a similar level through Treatment Period 1, with the number of hypoglycemia events (PG <70 mg/dL or 3.9 mmol/L) during Weeks 2-4, as detected by SMPG following a Poisson distribution with a mean of 9. The trial is powered to detect a treatment effect of 50%, hence, assuming that the number of hypoglycemia events reported for patients in the dasiglucagon group during Weeks 2-4 will follow a Poisson distribution with a mean of 4.5. At the final analysis, 32 patients will have 99% power testing at a 0.05 significance level. The overall alpha level is strongly controlled in this setting, remaining at or below 0.05.

This sample size was calculated before cancellation of interim analysis, this is why it refers to interim analysis. Cancellation of interim analysis (see Section 10), does not imply new sample size calculation.

3.3. Study Population

The study population consists of male and female patients between the ages of 3 months and 12 years (inclusive) with established CHI and experiencing ≥ 3 events of hypoglycemia per week despite SOC medication. Patients are to have previously undergone sub-total pancreatectomy or being treated with a non-surgical approach, having been evaluated as not eligible for pancreatic surgery.

3.4. Treatments Administered

In Treatment Period 1, patients will receive SOC only or dasiglucagon + SOC for 4 weeks based on their treatment assignment. In Treatment Period 2, all patients will receive dasiglucagon + SOC for 4 weeks.

Dosing of dasiglucagon will approximate continuous infusion by delivering small doses at frequent intervals via the infusion pump.

The pump administers 0.000025 mL/dose ~ 0.1 µg/dose (4 mg/mL formulation):

- 10 µg/hour ~ 0.5 µg every 3 min
- 20 µg/hour ~ 1 µg every 3 min
- 30 µg/hour ~ 1.5 µg every 3 min
- 40 µg/hour ~ 2 µg every 3 min
- 50 µg/hour ~ 2.5 µg every 3 min
- 60 µg/hour ~ 3 µg every 3 min
- 70 µg/hour ~ 3.5 µg every 3 min

Dasiglucagon treatment will be initiated at 10 µg/hr (t=0). Every 2 hours (t=2, 4, 6, etc.), the dose will be increased by an additional 10 µg/hr until either:

- 1) The patient is weaned off entirely from gastric dextrose infusion and/or glucose-fortified feeds, or
- 2) PG during the last 2 hours was consistently above 120 mg/dL (6.7 mmol/L), or
- 3) The maximum trial drug product infusion rate of 70 µg/hr is reached, or
- 4) AEs emerge that are considered to be related to dasiglucagon (e.g., nausea and vomiting) and limit further dose escalation

The dose of dasiglucagon should not be escalated beyond reaching the treatment objectives of PG in the range of 70-120 mg/dL (3.9-6.7 mmol/L) while approaching a normal feeding regimen according to age.

The 2-hour dose-adjustment interval will allow plasma drug levels to approach approximately steady-state before the dose is further increased. **Table 1** describes maximum dose a patient can be administered over 24 hour period.

The maximum dose of dasiglucagon should not exceed 70 µg/hr (1.68 mg/day) per day and the dose can be optimized based on each patient's treatment after the first 24 hours of dose administration.

Table 1: Initial 24-hour Maximum Dose of Dasiglucagon

Time (hours)	0	1	2	3	4	5	6	7	8	9	10	11
Dose (µg)	10	10	20	20	30	30	40	40	50	50	60	60
Cumulative dose (µg)	10	20	40	60	90	120	160	200	250	300	360	420

Time (hours)	12	13	14	15	16	17	18	19	20	21	22	23
Dose (µg)	70	70	70	70	70	70	70	70	70	70	70	70
Cumulative dose (µg)	490	560	630	700	770	840	910	980	1050	1120	1190	1260

3.5. Method of Assigning Patients to Treatment Groups

In Treatment Period 1, patients will be randomly assigned in a 1:1 ratio to receive either SOC only or dasiglucagon + SOC for 4 weeks using a block randomization scheme stratified by region United States (US)/non-US). In Treatment Period 2, all patients will receive dasiglucagon + SOC for 4 weeks. The stratification by region addresses the difference in practice of treatment for CHI, especially the prominent difference in frequency of sub-total pancreatectomy for diffuse CHI between US/non-US.

3.6. Blinding and Unblinding

This is an open-label trial. During parts of Screening, Treatment Period 1, and Treatment Period 2, patients will have CGM performed but the results will be masked.

3.7. Schedule of Events

A detailed schedule of events for the study is provided in [Table 2](#).

Table 2: Schedule of Events

Trial Period	Screening	Treatment Period 1					Treatment Period 2				Follow-up
		1 ^b	Telephone Call ^c	2	4	5 ^d	Telephone Call ^c	6	9		
Week											12
Day		1		8	22	29		36	57		85
Time window (days)	Day -28 to -14 ^a	±2		±2	±2	±2		±2	±2		±5
Visit #	1	2		3	4	5		6	7 ^e		8
General assessments											
Informed consent/assent	X										
Inclusion/exclusion criteria	X	X									
Randomization criteria		X									
Demography	X										
Body weight and length/height ^f	X	X				X			X		X
Medical history (including current illness)	X										
Concomitant medication	X	X		X	X	X		X	X		X
Safety Assessment											
Electrocardiogram	X	X ^r		X		X ^r		X	X		X
Echocardiography	X ^g								X		X
Vital signs ^h	X	X ^s		X	X	X ^s		X	X		X
Serum Pregnancy test ⁱ	X								X		X
Adverse events		X	X	X	X	X	X	X	X		X
Local tolerability		X		X	X	X		X	X		
Physical examination and neurological examination	X	X		X	X	X		X	X		X
Laboratory Assessments											
Clinical laboratory test ^j	X			X		X		X	X		X
Antibodies ^k		X ^l				X			X		X ^k
Pharmacokinetics/drug exposure								X	X		

Trial Period	Screening	Treatment Period 1					Treatment Period 2					Follow-up
		1 ^b	Telephone Call ^c	2	4	5 ^d	Telephone Call ^c	6	9	12		
Week		1		8	22	29		36	57	85		
Day		1		±2	±2	±2		±2	±2	±5		
Time window (days)	Day -28 to -14 ^a	±2		±2	±2	±2		±2	±2	±5		
Visit #	1	2		3	4	5		6	7 ^e	8		
Efficacy												
Continuous glucose monitoring	X (for at least 14 days prior to randomization)						Continuous ^m					
Self-monitored plasma glucose	X (for at least 14 days prior to randomization)						X (at least 3 times daily)					
Fasting tolerance test ^h	X (during active CGM period)					X ^o						
Trial Materials and reminders												
Randomization		X										
Dispense patient diary	X ^p	X		X	X	X		X				
Diary review		X		X	X	X		X	X			
QoL questionnaires ^q		X				X			X	X		
Dispensing of trial product		X		X	X	X		X				

Abbreviations: CGM = continuous glucose monitoring; PG = plasma glucose; QoL = quality of life; SMPG = self-monitoring of plasma glucose; SOC = standard of care; SpO₂ = blood oxygen saturation level; W = week

Note: An unscheduled visit can occur at any time if the investigator deems it necessary for patient safety.

- a Screening must occur within a minimum of 14 days to allow for solid baseline assessment.
- b At the beginning of Treatment Period 1 (Week 1), all patients will be hospitalized for 1-2 days. Patients assigned to SOC plus dasiglucagon treatment will be initiated and titrated on dasiglucagon, trained in the use of the infusion pump, and supervised. Patients assigned to SOC alone will receive a similar degree of supervision alongside the training in the use of the infusion pump. This period can be extended for both treatment groups if dasiglucagon titration has not been finalized or if training of the family/caregivers has not been completed satisfactorily.
- c Patients will be contacted by the investigator by telephone the day after discharge. The investigator will ask the parent(s)/guardian if they have any questions about the trial procedures and whether their child has experienced any AEs.
- d In Treatment Period 2, patients who were assigned to SOC treatment only in Treatment Period 1 will be hospitalized for the first 1-2 days of Week 5.
- e Visit 7 can be used as the first visit for Trial ZP4207 17106 (long-term extension trial) if the patient is continuing in long-term extension trial.
- f Length/height will be measured at Screening only.
- g An echocardiogram performed within 1 month of screening can be used.
- h Vital signs include blood pressure, heart rate, respiratory rate, and SpO₂.
- i A serum pregnancy test will be performed for girls of childbearing potential.
- j Clinical laboratory tests include hematology and biochemistry.
- k Any anti-dasiglucagon antibody-positive patient (treatment induced or treatment boosted) will be monitored at an additional follow-up visit, preferably 16 weeks after the last ADA-positive sample. Patients completing the trial before the ADA screening and confirmatory assays have been approved by the FDA and who do not continue treatment in the long-term extension trial will have this additional visit 16 weeks after the end of trial visit (Visit 8).
 - l The sample for ADAs should be taken prior to dosing of dasiglucagon in Treatment Period 1.
 - m Continuous glucose monitoring is required during Weeks 2-4 of Treatment Period 1 and Weeks 6-8 of Treatment Period 2.
 - n The fasting tolerance test will be stopped when PG is ≤ 60 mg/dL (3.3 mmol/L) and then ketones, insulin, and free fatty acids will be measured.
 - o The fasting tolerance test at Visit 5 should take place before initiation of dosing in Treatment Period 2 but while the patient is still on CGM.
 - p At screening, dispense diary and instruct patients' parent(s)/guardian in its use. At all other visits, the parent(s)/guardian will return the completed diary and obtain a new one.
 - q The PedQL (parent-reported versions) and CHI disease-specific questionnaires should be the first assessments performed at each visit.
 - r ECG should be performed at the start of the visit and at 24 ± 4 hours after initiation of trial drug for patients initiating treatment.
 - s Vital signs should be measured at the start of the visit and at 6 ± 1 , 12 ± 2 , and 24 ± 4 hours after initiation of the trial drug for patients initiating treatment.

4. Statistical Analysis and Reporting

4.1. Introduction

Data processing, tabulation of descriptive statistics, calculation of inferential statistics, and graphical representations will be performed primarily using SAS (release 9.4 or higher). If the use of other software is warranted, the final statistical methodology report will detail what software was used for what purposes.

Continuous (quantitative) variable summaries will include the number of patients (n) with non-missing values, mean, standard deviation (SD), median, minimum, and maximum.

Categorical (qualitative) variable summaries will include the frequency and percentage of patients who are in the particular category or each possible value. In general, the denominator for the percentage calculation will be based upon the total number of patients in the study population for the within each treatment group, unless otherwise specified. The denominator for by-visit displays will be the number of patients in the relevant study population with non-missing data at each visit.

The minimum and maximum will be reported with the same degree of precision (ie, the same number of decimal places) as the observed data. Measures of location (mean and median) will be reported to 1 degree of precision more than the observed data and measures of spread (SD) will be reported to 2 degrees of precision more than the observed data.

Percentages will be presented to 1 decimal place, unless otherwise specified.

Unless otherwise indicated, all testing of statistical significance will be 2-sided with a significance level of $\alpha = 0.05$ (see Section [10 Changes from Planned Analysis](#)).

4.2. Interim Analysis and Data Monitoring

4.2.1. Interim Analysis

No interim analysis is planned.

4.2.2. Data Monitoring Committee

A Data Monitoring Committee (DMC) will be established to conduct reviews of patient safety. It is expected that DMC meetings will occur 3 times a year during the course of the study. The reviews will monitor for issues that may justify modifying, suspending, or terminating the study.

The sponsor may request additional reviews, e.g., should any other findings/issues pertaining to safety or efficacy emerge requiring DMC review. Details of the operation of the DMC will be developed in conjunction with the members of the DMC before the first meeting and will be modified as required.

Although this is an open-label study with respect to treatment assignment, CGM data collected during the course of this study will be masked as well as randomized treatment group. The CGM data will be masked for preserving standard of care, not for treatment blinding.

The DMC analysis will be performed by an independent statistician who is not the author of this plan. The independent statistician has the real randomization available and will receive the unmasked CGM data from the vendor and scramble the results for the blinded team, thus maintaining the mask. The blinded statistician will prepare the outputs for the DMC reports based on dummy randomization and masked CGM data. He will provide SAS programs for the independent statistician to use. The independent statistician will prepare the aggregate outputs based upon unmasked CGM data and real randomization list. He will provide the outputs to DMC members.

. The study team (excluding the project statistician and programming team) will see only DMC summary tables aggregated over all patients (i.e., not split by treatment) until the final database lock.

4.2.3. Zealand Pharma Safety Committee

An internal Zealand Safety Committee is constituted to perform ongoing safety surveillance of clinical trials with dasiglucagon, including this trial.

If safety signals or concerns are observed, whether based on reported serious AEs (SAEs), review of all AEs and laboratory parameters reported, or any other notification of significant findings, the Safety Committee will respond appropriately to protect the safety of the patients. The Safety Committee meets quarterly and additionally on an ad hoc basis as needed.

The data package will be delivered based on Appendix 6 of the Pharmacovigilance Agreement; the shells for the data package will be provided in a separate document.

5. Analysis Populations

The following analysis populations are planned for this study:

- **Safety Set (SAF):** The Safety Set is defined as all patients administered with any randomized treatment. All patients randomized to “Standard of Care Only” group will be included in Safety Set. This population will be used to provide descriptive summaries of safety data. Patients will be summarized by treatment period according to treatment received.
- **Full Analysis Set (FAS):** The FAS includes all patients in the Safety Set who have a valid (non-missing) baseline primary efficacy assessment (i.e., baseline SMPG-detected hypoglycemia episode rate). This population will be used to analyze efficacy data. Patients will be analyzed by treatment period according to planned treatment.
- **Per Protocol (PP) Analysis Set:** The PP Set will include all patients in the FAS without any major protocol deviations. This population will be used to analyze primary and key secondary endpoints as a supportive analysis. Patients will be analyzed according to planned treatment for the first treatment period only.
- **Pharmacokinetic (PK) Analysis Set:** The PK Set will include all patients in the Safety Set who have at least 1 measurement with quantifiable plasma concentration of dasiglucagon. This population will be used to provide descriptive summaries of PK data. Patients will be summarized according to treatment received.

6. General Issues for Statistical Analysis

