8.2.3. Randomization Exclusion Criteria

- 1. Use of glucagon within 24 hours before randomization.
- 2. Significant changes to CHI medications during screening.
- 3. An average of <3 events per week of hypoglycemia, as recorded in the diary during the 2 weeks prior to randomization.

The Randomization Visit may be rescheduled if randomization Exclusion Criterion 1 is met.

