8.1. Primary Efficacy Analysis

8.1.1. Primary Analysis for the Primary Endpoint

The primary efficacy endpoint is the SMPG-detected hypoglycemia episode rate during Weeks 2-4 of Treatment Period 1. A hypoglycemia episode is defined as PG <70 mg/dL or 3.9 mmol/L, as detected by SMPG. The analysis will be based on the hypoglycemia episodes reported in the eCRF. Baseline SMPG-detected hypoglycemia episode rate is defined as the average weekly number of hypoglycemia episodes during the 2-week baseline period. Hypoglycemia episode rate in Weeks 2-4 of Treatment Period 1 is defined as the average weekly number of hypoglycemia episodes across the last 3 weeks of the treatment period. The hypothesis:

H_{11} : SMPG-detected hypoglycemia episode rate $_{\text{dasiglucagon}}$ = SMPG-detected hypoglycemia episode rate $_{\text{SOC only}}$

will be analyzed by using negative binomial regression, with region and treatment group as fixed effects, baseline hypoglycemia rate as a covariate and number of hypoglycemia episodes during weeks 2-4 as dependent variable. The log-transformed number of weeks in Weeks 2-4 of Treatment Period 1, after accounting for imputation (i.e., log(3) for subjects with imputed data, or number of weeks in Weeks 2-4 otherwise), will be used as an offset variable. The null hypothesis is that there is no difference in the incidence of average weekly number of hypoglycemia events between the 2 treatment groups, which will be tested at the significance level of $\alpha=0.05$.

The primary analysis will estimate the treatment effect based on the de facto (treatment policy) estimand. All available data in the form of actual measurements will therefore be included in the analysis, irrespective of adherence to treatment or use of subsequent therapy. Missing data will be imputed using the MI methodology as described in Section 6.1.4.2. In case of no missing data, primary analysis will be run without multiple imputation.

Descriptive statistics for observed and change from baseline in incidence of average weekly number of hypoglycemia events between the 2 randomized treatment groups will be presented. The study weeks presented will be Baseline, Week 1, Week 2, Week 3, Week 4, and Week 2-4. No imputation of missing data will be performed for descriptive statistics.

A graph will be provided showing the mean number of weekly hypoglycemia events for each treatment group.

This analysis will be conducted on patients in the FAS.

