9.8. Concomitant Medication

Concomitant medications will be coded using World Health Organization Drug Dictionary Enhanced (WHO-DDE) (Version September 01, 2018 or later) thesaurus.

Medications that started before first dose of dasiglucagon (dasiglucagon + SOC treatment group) or randomization (SOC only treatment group) will be considered prior medications if they were stopped before first dose of dasiglucagon/randomization. Any medications ongoing at start of trial will be considered to be concomitant medication ongoing at start. If a medication starts during the trial it will be considered as medication starting during the trial.

Concomitant Medication are described on the FAS according to randomized treatment.

Frequencies and percentages will be summarized descriptively by Anatomical Therapeutic Chemical (ATC) classification Level 4 and Preferred Name, if applicable, by overall patients and treatment group within treatment period. The summary will be presented in descending order of frequency of ATC and then Preferred Name within ATC based on overall patients.

10. Changes from Planned Analysis

- The protocol mentioned how to handle analyses involving trial site; however, since randomization is stratified by region (US vs non-US), region will be included in the analyses (it is not included in the protocol). Thus no analyses will be performed by trial site.
- The Full Analysis Set definition was clarified to indicate that the primary endpoint baseline assessment needs to be non-missing for a patient to be included in the set.
- A PK Set was added to support summaries of PK data.
- In the protocol a common methodology for the imputation of missing data for primary and key secondary endpoints was described. This has been split into appropriate methods for imputing missing event data based on the negative binomial model and non-event data based on the MCMC method for non-monotone missing data and sequential regression for monotone missing data.
- Baseline for endpoints related to external CGM data will be defined taking into account data from 14 days before randomization, those days will not necessary be consecutive, this is different from baseline definition of the other endpoints.

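### SAP 5 does not say whether a child randomised to dasiglucagon who never starts it belongs to the FAS; the more natural reading leaves the child out, which fits poorly with the treatment-policy estimand

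*SAP*

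**What the plan says.** The relevant rules are these.

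- **Safety Set (SAP 5).** "The Safety Set is defined as all patients administered with any randomized treatment". A further sentence states that every patient randomised to the Standard of Care Only "group will be included in Safety Set". The dasiglucagon arm has no such sentence.
- **FAS (SAP 5).** "The FAS includes all patients in the Safety Set who have a valid (non-missing) baseline primary efficacy assessment". On allocation: "Patients will be analyzed by treatment period according to planned treatment". Protocol 12.3 (13.3 in the German version) nests the FAS in the Safety Set in the same way, but lacks the sentence about SOC-only patients.
- **Primary analysis (SAP 8.1.1).** "This analysis will be conducted on patients in the FAS". The estimand is de facto (treatment policy), using all actual measurements "irrespective of adherence to treatment or use of subsequent therapy".
- **Other analyses of the primary endpoint (SAP 8.1.2).** These are an analysis without imputation, a repeat on the PP Set (a subset of the FAS), and a possible ad hoc exclusion of data after drug discontinuation. None covers all randomised patients.
- **Day 1 (SAP 6.1.7).** In the dasiglucagon arm it is the day the drug is first initiated. In the SOC-only arm it is the randomisation date.

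**The concern.** The treatment-policy effect is normally understood over everyone randomised, whatever they then took. If a child allocated to dasiglucagon never starts and drops out of the FAS, the primary analysis compares starters in one arm with all patients in the other. Whether to start is settled after randomisation, with the allocation known, and the SOC-only arm has no corresponding filter. Any observed counts for that child would go unused, although protocol 8.4 (9.4 in the German version) asks patients who stop treatment to stay on the visit schedule.

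There is also a smaller gap. A dasiglucagon patient who is never dosed has no Day 1 as SAP 6.1.7 defines it, and some of the analysis windows are counted from Day 1.

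**Working it through.** **1. Which FAS condition could remove anyone?** There are two: Safety Set membership and a non-missing baseline rate. The second should rarely matter, because protocol 8.2.3 already bars randomisation for "An average of <3 events per week of hypoglycemia, as recorded in the diary during the 2 weeks prior to randomization", so a correctly randomised child should have two weeks of counts. SAP 10 adjusted only that condition: "The Full Analysis Set definition was clarified to indicate that the primary endpoint baseline assessment needs to be non-missing". The nesting was left as it was.

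**2. Is a never-dosed dasiglucagon patient in the Safety Set?** Two readings are possible.
- *Excluded:* the drug was not administered. In support, the SOC-only sentence would be unnecessary if background SOC were enough. Elsewhere the SAP ties the active arm to first dasiglucagon and the SOC arm to randomisation (Day 1 and TEAE in 6.1.7, prior medication in 9.8).
- *Included:* the randomised treatment in that arm is SOC plus dasiglucagon (protocol 9.2), so a child on SOC has received part of it.

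The first reading is more natural. Neither is stated.

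**3. Which windows fail?** Weeks 2-4 are counted back from the Week 5 visit, so an undosed child who attends that visit has a defined window. The baseline and Week 1 windows use the Day 1 visit date, which such a child also has. Only the early-termination table, which counts forward from Day 1, has no starting point.

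**4. Does the imputation need the exclusion?** No. With zero time in Treatment Period 1, the SAP 6.1.4.2 formulas give ŷ₁ = 0 and p_cond = k/(k + ŷ₂). The Week 1 rule scales the imputed count by 1 − 7/28 = 21/28.

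**5. The plan's power figure.** Inputs from SAP 3.2 and 3.5: 32 patients at 1:1 (16 per arm), Poisson means 9 and 4.5, two-sided α = 0.05.
- SE = √(1/(16×9) + 1/(16×4.5)) = 0.1443
- Power = Φ(ln 2/0.1443 − 1.96) = 99.8%, consistent with the stated 99%.

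**6. Size with m non-starters.** Assumption, since the documents give no number: m of the 16 never start, and they have the SOC mean of 9. The all-randomised dasiglucagon mean is (4.5×(16 − m) + 9m)/16.

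| m | Mean | All-randomised ratio | SE | Power, all randomised | Power, FAS excluding them (ratio 0.50) |
|---|---|---|---|---|---|
| 0 | 4.500 | 0.500 | 0.1443 | 99.8% | 99.8% |
| 1 | 4.781 | 0.531 | 0.1415 | 99.4% | 99.7% |
| 2 | 5.063 | 0.563 | 0.1389 | 98.5% | 99.6% |

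Simulating the same Poisson cases with the dispersion estimated gives 99.0% and 97.3% for m = 1 and 2, all randomised.

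**7. Bias under no drug effect (illustrative).** The planned negative binomial model was simulated with assumed frailty variance 0.5, residual dispersion 0.3 and a SOC mean of about 9. The ratio from the FAS divided by the ratio from all randomised patients was:
- 1.002 to 1.004 when non-starting depended on baseline rate (1.005 to 1.011 in a second run with SOC mean 13.3);
- 0.95 and 0.92 when the 1 or 2 children with the highest true rates never started;
- 1.04 and 1.07 when those with the lowest true rates never started.

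The largest shift, ln(0.915) = −0.089, is about 0.3 of the sampling SD of the log ratio (0.29).

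**The case against.** **The exclusion is inferred.** This stands. The protocol definition lacks the SOC-only sentence, so that sentence may only clarify that patients with no study-drug record still count. A reader might infer that the SAP expressly removes non-starters; it does not.

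**The estimand conflict is partly interpretation.** This stands in part. SAP 8.1.1 applies treatment policy to which data are used, and the same section names the FAS as the population. Neither document defines the estimand population as all randomised patients. Protocol 8.4 addresses patients who stop, not those who never start. The mismatch is a poor fit, not a contradiction in terms. Even so, using data irrespective of adherence while dropping the least adherent patients in one arm is hard to defend.

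**The case is hypothetical.** This stands. Randomisation and dispensing share Visit 2, infusion starts in hospital, and no non-starter is reported. SAP 7.1 would show the set sizes and a CONSORT diagram.

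**Exclusion favours dasiglucagon.** A reader might infer this from 0.50 against 0.53 or 0.56. Those figures describe two different effects when the drug works. With no drug effect, exclusion shifts the ratio only if non-starting tracks prognosis that baseline misses, and the shift can go either way.

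**Part of the SAP was not available.** Some text around SAP 10 and 11 was removed, so the absence of an all-randomised analysis is established only for the visible text.

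**Conclusion.** The point holds as a gap in the FAS definition, with low severity. SAP 5 leaves a never-started dasiglucagon patient unclassified. On the more natural reading, an open-label post-randomisation event can remove patients from one arm only, and no visible analysis restores them. The effect is nil if every child starts, which is likely.

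The ratios of 0.53 and 0.56 rest on the assumption that 1 or 2 of 16 never start and have the SOC rate. The null-bias figures rest on assumed overdispersion and on extreme selection. Power under overdispersion would be lower throughout, but it depends on a dispersion the documents do not give, so any such figure is illustrative only. The documents do not support a claim that the planned result is biased or that the trial is underpowered for this reason. The case for acting is that the rule is unclear, one-sided on its natural reading, and easy to settle before a real case arises.

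**What to change.** Before database lock:

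1. **SAP 5.** Define the FAS as all randomised patients with a non-missing baseline SMPG-detected episode rate, analysed as randomised. Keep the Safety Set for safety only. Require at least one dose for dasiglucagon patients in the PP Set, so that set does not widen.
2. **SAP 6.1.7.** For a dasiglucagon patient never dosed, set Day 1 to the randomisation date, so that the early-termination windows have a start.
3. **SAP 6.1.4.2 and 6.1.4.3.** Use a non-starter's observed data and apply the existing jump-to-control imputation only to missing time. Both sections are needed because the key secondary endpoints use the same FAS. A patient with no observed time cannot contribute to the Step 1 fit in 6.1.4.2 and is imputed at the SOC rate.
4. **SAP 10.** Record this as a departure from protocol 12.3 (13.3 German), which contains the same nesting. SAP 10 already records other departures, including the addition of region to the analyses.

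If the sponsor intends non-starters to be in the FAS already, say so in SAP 5 and still make changes 2 and 3.

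The cost is a few lines of SAP text and a small programming rule, with no new data. Such a child would also enter the Treatment Period 2 FAS summaries. If anyone never starts, the estimate is likely to be slightly less favourable. Power under the plan's Poisson means would be about 99.4% or 98.5% with 1 or 2 non-starters, against 99.8% with none.
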